9.5.1.1 Assumptions used for the sample size and power calculations

To estimate the number of anifrolumab exposed SLE pregnancies and the expected number of primary study outcome events in data sources that would be eligible for the analysis in this study, the following assumptions were used:

- **A prevalence of 7% for MCM outcome.** Prevalence of MCM in pregnancies in women with moderate-to-severe SLE was estimated based on a literature search. Among moderate/severe SLE patients exposed to belimumab, birth defect prevalence estimates of 5.6% to 21.7% were observed in post hoc summary of clinical studies and a prospective

pregnancy registry, respectively (86) A prevalence of 6.4% of congenital malformations was observed in renal SLE pregnancies (51) These proxy estimates of MCM in moderate-to-severe SLE align with the observed population based prevalence estimates ranging from 7.4% to 13.6% (114) among women diagnosed with SLE (117).

- **A prevalence of 20% for the composite of select pregnancy loss outcomes (composite of spontaneous abortion and stillbirth).** Prevalence of the composite outcome of select pregnancy loss (spontaneous abortion and stillbirth) in moderate-to-severe SLE pregnancies ranged from 15.3% to 30% (51, 81, 86). For the individual outcomes, the prevalence estimates ranged from 1.8% to 3.7% for stillbirths (51, 103, 120), and the prevalence estimate was 16% (12.1% to 19.9%) for spontaneous abortions (103). Based on the intended objective to evaluate embryo-foetal loss, a composite outcome of spontaneous abortion and stillbirth has been used.
- **Proportion of SLE pregnancies occurring in women with moderate-to-severe disease of 50%.** There is limited information on the proportion of SLE pregnancies that occur in women with moderate-to-severe disease. The proportion of moderate-to-severe disease at the time of diagnosis among the general SLE population is estimated to be 50% (66, 80). Literature regarding medication patterns for SLE pregnant women suggests that 40-45% use immunosuppressors and/or biologics, which may be a proxy indicator of moderate/severe disease (12, 67). Thus, in this study, an assumption of 50% was used.

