- **Proportion of unexposed to confirmed teratogenic SLE SOC and/or non-SLE SOC drugs of 80%.** It is estimated that 80% of the SLE pregnancies are not exposed to SLE SOC and non-SLE SOC confirmed teratogenic drugs before conception, with a time period of 5-half-lives of relevant drug (see list of confirmed teratogenic drugs and half-lives in Table 20), or during pregnancy. This estimate is based on the reported use of SLE SOC and/or non-SLE SOC drugs in SLE population (47, 48).
- **Proportion of anifrolumab exposure during the first trimester of pregnancy of 80%.** The majority of the anifrolumab exposed pregnancies are expected to be unplanned and exposed to anifrolumab only in the early stages of the pregnancy, as the current recommendations indicate that anifrolumab should only be used during pregnancy if the benefit outweighs the risk to the foetus (86). We therefore used the assumption that 80% of all anifrolumab exposed pregnancies are exposed to anifrolumab during the first trimester of pregnancy.
- **Proportion of anifrolumab exposed pregnancies in women with moderate-to-severe SLE of 5% and 10%.** Based on market forecasts, uptake of anifrolumab in the general SLE population is expected to grow from 5% within two years of market launch to 20% by 5 years after market launch. Given the uncertainty of how these forecasts apply to SLE women of child-bearing potential and to use in pregnant SLE women, we used a conservative lower bound (5%) and a more realistic midpoint value (10%) for the proportion of pregnancies in women with moderate-to-severe SLE exposed to anifrolumab.

In addition, to estimate the minimum required sample size and the expected power, the following assumptions were used:

- **Non-inferiority margin of RR of 2.5.** The RR of 2.5 was based on previously reported increase in risk of MCM for exposure to a major teratogenic drug (62).

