9.5.1.3 Methods for estimating required sample size and expected power

The required sample size and expected power calculations were based on the assumptions described above and were carried out separately for each primary outcome (MCM and select pregnancy loss) at the meta-analysis level. Data sources that had at least a 90% probability of having at least 1 event in each exposure group (see [Table 10](#) and [Table 11](#)) were included in the meta-analysis.

The sample size and power calculations were performed using simulations under the assumption that the true RR is 1.0. For both sample size and power calculations, simulations were repeated 1,000 times to get 1,000 simulated 95% CIs for RRs.

The required sample size to achieve 80% power for a one-sided alpha-level of 2.5% at meta-analysis were performed using simulations as detailed below:

1. For a given overall sample size, a proportion of the overall population was assigned to each of the data sources likely to be included in the meta-analysis (proportions are presented in [Table 12](#)).
2. The number of primary outcome events in each exposure group were randomly drawn for each data source from a binomial distribution. In the binomial distribution, the number of trials was set equal to the estimated data source-level sample size and the probability of success was set to equal to the prevalence of the outcome in each exposure group, assuming that the true RR is 1 (no effect of exposure).
3. The estimated data source level log(RRs), their standard errors, and their 95% CIs were computed using a log-link Poisson regression (in place of log-binomial regression which tended to not converge) from the simulated number of events.
4. The data source level log(RRs) and their standard errors were entered in a fixed-effect meta-analysis model where pooled 95% CIs were computed. The inverse-variance method was used for the meta-analysis. The meta-analysis was run using the meta package in R ([97](#)).
5. The steps 2-4 were repeated for 1,000 times, and the proportion (which represents the achieved power) of the 1,000 simulated 95% CI upper bounds that were smaller than the target RR of 2.5 was computed.
6. The overall sample size was varied to range over positive integers for simulations, and the required sample size for this study was identified as the minimum overall sample size necessary to achieve 80% power (as defined in step 5).

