The achieved power (proportion of the simulations where the upper bound of the meta-analysis RR was lower than the target RR of 2.5) was estimated based on the anticipated number of primary outcome events in each exposure groups and using simulations where the steps 2-4 (as described above) were repeated 1,000 times to get 1,000 simulated 95% CIs for RRs. The achieved power was calculated as the proportion of the 1,000 simulated 95% CI upper bounds that were smaller than the target RR of 2.5.

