The rationale of this sensitivity analysis is to examine the robustness of the primary study outcome (MCM and select pregnancy loss outcomes) analysis results to unmeasured confounding. Quantitative bias analysis methods will be used for studying the effect of unmeasured confounding on the study results (68). The quantitative bias analysis methods will be selected depending on what is known about the potential unmeasured confounder and its relationship between the exposure and the primary study outcomes (26). If the effect of a specific confounder and its relationship between the exposure and the primary study outcomes is well understood, a simple equation may be used for quantifying the confounder's relationship to exposure and primary study outcomes. This method allows to estimate the primary study outcome analysis results after adjusting for the specific unmeasured confounder (26). This approach could be considered in cases where a specific confounder is measured in some but not all data sources (listed as a limitation in Section 9.9). In case nothing is known about a potential unmeasured confounder, methods such as the E-value approach may be considered (26). The E-value approach aims to assess how strongly an unmeasured confounder would have to be related to anifrolumab exposure and primary study outcomes to explain away (i.e., nullify) the observed association of anifrolumab exposure with the primary study outcomes (112). Further details on the methods will be provided in the SAP.

Account for actual use of SLE SOC during pregnancy

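### The E-value in Section 9.7.5 is referenced only to RR 1, so for a result that rules out RR 2.5 it does not show how robust that conclusion is

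*Protocol*

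**What the plan says.** Section 9.7.5 plans a quantitative bias analysis for unmeasured confounding of the two primary outcomes. Where a confounder is well understood, a simple equation gives a bias-adjusted result. Where nothing is known about the confounder, the E-value is named as an option. It is described as how strongly "an unmeasured confounder would have to be related to anifrolumab exposure and primary study outcomes to explain away (i.e., nullify) the observed association". The reference value is therefore RR 1; 2.5 is not mentioned there. Further detail is left to the SAP.

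The study-size sections use a different reference. Section 9.5.1.1 sets a "Non-inferiority margin of RR of 2.5". Section 9.5.1.3 states: "The sample size and power calculations were performed using simulations under the assumption that the true RR is 1.0". It then defines power: "The achieved power was calculated as the proportion of the 1,000 simulated 95% CI upper bounds that were smaller than the target RR of 2.5". Sections 9.5.2 and 9.5.3 give required sizes and expected power for ruling out 2.5. The ENCePP checklist (Appendix B, item 2.1.4) points to Sections 8.1 and 9.5 for the hypotheses to be tested.

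**The concern.** A robustness check should be referenced to the conclusion it tests. The result for which the study is sized is a pooled RR near 1 with an upper bound below 2.5. For that result there is little or no association to nullify. The open question is how strong confounding would have to be to hide a true RR of 2.5, and an E-value to RR 1 does not answer it.

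The question is a practical one here. Section 9.9 concedes that residual confounding may remain. Table 17 shows no pre-pregnancy BMI, smoking, or alcohol and substance data for France, and no socioeconomic status for Carelon. These are two of the three sources expected to contribute to the meta-analysis of major congenital malformations (MCM). A reader given only the null-referenced figure could take a weaker safety result for a more robust one.

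**Working it through.** **Inputs from the protocol.** Margin 2.5; one-sided alpha 2.5%; true RR 1.0; MCM prevalence 7% and pregnancy loss 20% (Section 9.5.1.1); fixed-effect inverse-variance pooling (Section 9.5.1.3). Exposed numbers at 10% uptake in 2032 (Table 11): MCM 102 + 114 + 116 = 332; loss 163 + 162 + 11 + 145 = 481. Allocation 1:2.

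**Reproducing the plan's figures.** Simulation as in Section 9.5.1.3, with 100,000 runs, SE of log RR per source = sqrt(1/a + 1/b) for a exposed and b unexposed events, and sources with a zero cell dropped:
- MCM, 210 exposed at 1:2: power 80.4% (plan: 80%).
- MCM, 10% uptake: 96.0% at 1:2 and 98.2% at 1:3 (plan: 96% and 98%).
- MCM, 5% uptake, 1:2: 66% (plan: 69%), the loosest match of those checked. The closed form gives 72%, and the plan's 1,000 runs carry a simulation error of about 1.5 points.

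**Formulas.** The protocol gives no E-value formula, so the standard one is used. To the null, E = R + sqrt(R(R − 1)), with R = RR, or 1/RR if RR is below 1. For an interval, the same formula is applied to the limit nearer 1, and E = 1 if the interval contains 1. To the margin, B = 2.5 / upper 95% bound and E = B + sqrt(B(B − 1)), for B > 1.

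**Interval-based value.** Among simulated results that rule out 2.5 (10% uptake, 1:2, true RR 1), the interval contains 1 in 98.8% for MCM and 97.4% for loss. In all of these the null-referenced interval E-value is 1, however far the upper bound lies below 2.5.

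**Point-estimate value, MCM.** SE = sqrt(1/(332 × 0.07) + 1/(664 × 0.07)) = 0.254, so the upper bound is RR × exp(1.96 × 0.254) = RR × 1.645.

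| Pooled RR | Upper 95% bound | E to RR 1, point | E to RR 1, interval | E, upper bound to 2.5 |
|---|---|---|---|---|
| 0.8 | 1.32 | 1.81 | 1 | 3.21 |
| 1.0 | 1.65 | 1.00 | 1 | 2.41 |
| 1.2 | 1.97 | 1.69 | 1 | 1.85 |
| 1.4 | 2.30 | 2.15 | 1 | 1.39 |
| 1.5 | 2.47 | 2.37 | 1 | 1.13 |
| 2.0 | 3.29 | 3.41 | 1.73 | 2.5 not ruled out |

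For RR 1.5, for example: to the null, 1.5 + sqrt(1.5 × 0.5) = 2.37; to the margin, B = 2.5/2.468 = 1.013 and E = 1.013 + sqrt(1.013 × 0.013) = 1.13. The largest RR that still rules out 2.5 at this SE is 2.5/1.645 = 1.52. About 52% of the simulated MCM results that rule out 2.5 have RR above 1, where the two columns move in opposite directions. Below RR 1 they move together.

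**Point-estimate value, pregnancy loss.** SE = sqrt(1/(481 × 0.20) + 1/(962 × 0.20)) = 0.125, and the upper bound is RR × 1.277. At RR 1.0, B = 2.5/1.277 = 1.957 and E = 3.33. At RR 1.5, B = 2.5/1.916 = 1.305 and E = 1.94. The null value again rises from 1.00 to 2.37. Here an RR between about 1.28 and 1.96 both excludes 1 and rules out 2.5, so both E-values would be needed.

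**The case against.** The E-value is optional, and Section 9.7.5 leaves the choice of method and its details to the SAP. The margin stands only in the study-size material and its summaries: objectives 2 and 4 and Sections 9.7.1 and 9.7.2 estimate RRs with 95% intervals and state no test against 2.5. Section 9.9 names confounding by indication from disease severity or activity. If sicker women received anifrolumab, that would plausibly raise the RR, and then asking what would explain it away is the right question. The simple bias equation yields an adjusted result that can already be set against 2.5. Finally, most intervals containing 1 when the true RR is 1 is largely just 95% coverage.

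Much of this stands, and it limits the point. It does not remove it. The protocol does state a reference value, RR 1, and an SAP that follows it would inherit that choice. The bias equation is reserved for well-understood confounders; for unknown ones the E-value is the only method named. The coverage argument explains why the interval-based value is nearly always 1. It does not make that value informative about the margin.

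**Conclusion.** The point holds for a result that rules out 2.5. For such a result the null-referenced E-value does not measure robustness. The interval-based value is nearly always 1 if the true RR is 1. At a given SE, for pooled RRs between 1 and 2.5, the point-estimate value rises as the safety conclusion weakens.

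Three stronger readings are tempting and not supported:
- A reader might infer that the planned E-value is useless for safety. For an apparent harm signal it is the relevant figure: at RR 2.0 (interval 1.22 to 3.29) it is 3.41 for the estimate and 1.73 for the limit.
- A reader might infer that it orders every RR above 1 wrongly. Above 2.5 the point-estimate E-values to 1 and to 2.5 rise together (RR 3: 5.45 and 1.69; RR 4: 7.46 and 2.58).
- A reader might infer that the plan cannot test confounding against 2.5 at all. The bias equation can, for a known confounder.

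The sizes rest on the protocol's prevalences and 10% uptake, 1:2 allocation, the standard E-value formula and the SEs above. Propensity-score matching or weighting may change those SEs. The documents do not establish which way residual confounding would run.

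**What to change.** In Section 9.7.5, keep the E-value to RR 1 and add a margin-referenced one for the pooled adjusted RR of each primary outcome, since 2.5 was set at meta-analysis level. With B = 2.5 / upper 95% bound, report E = B + sqrt(B(B − 1)) when B > 1. When B is 1 or less, state that 2.5 is not ruled out and that the value does not apply. That case needs wording: with the plan's stated MCM power of 69% at 5% uptake and 1:2, it would arise in about 31% of studies even at a true RR of 1. Report both E-values side by side whatever the result. Apply the simple bias equation to the upper 95% bound as well as to the estimate, and compare the result with 2.5. The cost is a few lines of protocol or SAP text and one extra formula; no new data are needed.

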prescribed/dispensed (if information on the date of dispensation is not available, the start of the exposure period will be defined based on the date when the prescription was issued). The end date of the exposure period is calculated by adding the estimated window of clearance and expected supply to the prescriptions/dispensations/administrations date (Figure 6).

[figure not shown]

Figure 6: Anifrolumab exposure period

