as described in Section 9.7.1. In addition, meta-analysis on the data source specific crude and adjusted RRs of MCM in live and non-live offspring from mothers who were exposed or unexposed to anifrolumab during pregnancy will be conducted as described in Section 9.7.1.

Objective 3

The analysis to describe and estimate the risk of select pregnancy loss outcomes (composite of spontaneous abortion and stillbirth) in all pregnancies from the mothers who had moderate/severe SLE and were exposed or unexposed to anifrolumab during pregnancy (study objective 3) will be performed using the *pregnancy* cohort (as defined in Section 9.2.2). The crude and adjusted cumulative incidence (with corresponding 95% CI) of the select pregnancy loss outcomes (composite of spontaneous abortion and stillbirth) will be estimated for cases where mother was exposed to anifrolumab during pregnancy and for cases where mother was unexposed to anifrolumab during pregnancy. The crude cumulative incidence (i.e., risk) will be calculated as the total number of select pregnancy loss outcomes (composite of spontaneous abortion and stillbirth) divided by the total number of pregnancies. The adjusted cumulative incidence (i.e., risk) will be estimated following PS adjustment, if suitable for the data.

Objective 4

To estimate the relative risk of select pregnancy loss outcomes (composite of spontaneous abortion and stillbirth) in pregnancies from the mothers who had moderate/severe SLE and were exposed or unexposed to anifrolumab during pregnancy (study objective 4), the crude and adjusted RR (with corresponding 95% CI) will be estimated using the *pregnancy* cohort (as defined in Section 9.2.2). The crude RR and its 95% CI will be estimated using a regression model as specified in Section 9.7.1. The adjusted RR and its 95% CI will be estimated using the same regression model following an appropriate PS adjustment method as described in Section 9.7.1.

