The rationale for this sensitivity analysis is to account for actual use of SLE SOC during pregnancy in estimating the risk and relative risk of primary study outcomes. For the main analysis, the SLE SOC is assumed to be continued throughout pregnancy. In this sensitivity analysis, an exact matching criterion will be added to the PS matching step of the cohort building. For a given anifrolumab exposed pregnancy, the set of potential matches will be restricted to pregnancies unexposed to anifrolumab and exposed to SLE SOC during the same trimester(s) as the exposed pregnancy was exposed to anifrolumab. For example, if a given exposed pregnancy is exposed to anifrolumab during the second and third trimester, potential matches will be restricted to unexposed pregnancies with SLE SOC exposure during the second and third trimester. After matching, the sensitivity analysis will be conducted as described for Objectives 1-4 (see Section 9.7.2).

Exposure to anifrolumab and risk of MCM using the MACDP classification system for congenital malformations

This study comprises both European and American data sources; therefore, the MACDP USA-based classification system, in addition to the EUROCAT, for MCM will be used.

The MACDP classification system categorises and defines congenital malformations differently from EUROCAT, and the results obtained from each classification system may differ. Since it is essential to consider the potential impact of different categorisations and definitions of congenital malformations on the results, a sensitivity analysis will be performed using the MACDP classification system. The rationale of this sensitivity analysis is to examine the robustness and

reliability of the association between exposure to anifrolumab and the risk of MCM using the MACDP classification (59).

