- Misclassification may occur in the derivation of date of conception. When based on LMP, the derivation of date of conception assumes an average cycle length of 28 days and that conception occurred mid-cycle. The LMP is also subject to accuracy of recall by the woman, regularity of her cycles, and variations in the interval between bleeding and anovulation. When based on gestational age, the degree of misclassification depends on the method and accuracy of the gestational age assessment. However, the misclassification is expected to be within a range of days for most patients.

- Immortal time bias cannot be ruled out. Immortal time is the period during which the outcome of interest cannot occur because of the study design (108). In this study, there is an immortal time because a pregnancy must “survive” until initiation of treatment to be considered as exposed. Nevertheless, it is expected that most pregnant women would have exposure to anifrolumab in the first trimester, and exposure to anifrolumab initiation in the second or third trimester is not expected to be frequent. Adding to this, most outcomes that terminate a pregnancy, such as a spontaneous abortion or an ectopic pregnancy, are expected to happen in the first trimester, thus minimising the impact of this bias.
- The probability of receiving anifrolumab may be related to the length of pregnancy, to some extent. The patients with longer pregnancies have more opportunity (i.e., time) to be prescribed anifrolumab, while the patients with shorter pregnancies have less opportunity (i.e., time) to be prescribed anifrolumab. This may cause a bias in the analysis as shorter pregnancies are more likely to be included in the study cohort unexposed to anifrolumab.
- Both maternal and paternal disease history can be important predictors of the risk of adverse pregnancy outcomes because of shared environmental and genetic risk factors. For this study, no paternal data will be available because linkage to paternal data is not possible for most data sources. Therefore, offspring whose fathers have a history of CM before pregnancy will not be excluded, and no adjustments can be made for potential confounders related to fathers.

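### The 'actual use of SLE SOC' sensitivity analysis selects comparators on SOC use after follow-up starts; on the plain reading this pushes the pregnancy-loss risk ratio above 1 when there is no effect

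*Protocol*

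**What the plan says.** Protocol section 9.7.5 adds an exact-match condition to the propensity-score matching, to relax the main analysis's assumption that SOC continues throughout pregnancy. Under it, "the set of potential matches will be restricted to pregnancies unexposed to anifrolumab and exposed to SLE SOC during the same trimester(s") as the anifrolumab exposure. For a pregnancy exposed in trimesters 2 and 3, "potential matches will be restricted to unexposed pregnancies with SLE SOC exposure during the second and third trimester". Then: "After matching, the sensitivity analysis will be conducted as described for Objectives 1-4".

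For pregnancy loss, section 9.7.2 (Objective 3) defines crude risk as "calculated as the total number of select pregnancy loss outcomes (composite of spontaneous abortion and stillbirth) divided by the total number of pregnancies", and section 9.3.2 starts follow-up at LMP2. The sensitivity analysis has no landmark, no alignment on gestational age and no restriction of the time at risk.

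On exposure length, section 9.3.1 says: "The end date of the exposure period is calculated by adding the estimated window of clearance and expected supply" to the date of prescription, dispensation or administration. The clearance window for anifrolumab is 16 weeks. The same section lets exposure end early with a censoring event such as the end of the pregnancy.

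**The concern.** The trimesters in which a pregnancy was exposed are known only afterwards and depend on how long it lasted. An exposed pregnancy lost in trimester 1 can only be exposed in trimester 1, so its comparator needs SOC in trimester 1 and may or may not go on to a loss. An exposed pregnancy that survives with exposure running into trimester 2 must be paired with one that had SOC in trimester 2, hence one that also survived trimester 1. The exposed arm keeps all its early losses, while part of the comparator arm is chosen for having had none.

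Pregnancy loss is a primary outcome, and section 7.4 cites a non-significant excess of embryo-foetal loss in monkeys. A robustness check that gives an RR above 1 under no effect could appear to contradict the main result.

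The immortal-time limitation in section 9.9 does not cover this. It concerns exposed pregnancies having to survive until treatment starts, which biases the other way.

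**Working it through.** **Inputs from the protocol**
- Loss risk L = 0.20 (section 9.5.1.1: "A prevalence of 20% for the composite of select pregnancy loss outcomes").
- Share exposed in trimester 1 = 0.80 (same section: "80% of all anifrolumab exposed pregnancies are exposed to anifrolumab during the first trimester of pregnancy"). The other 20% are treated as late starters.
- Timing of losses: section 9.9 says only that most outcomes ending a pregnancy "are expected to happen in the first trimester, thus minimising the impact of this bias".

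**Assumptions**
- s, the share of losses falling in trimester 1: 0.8, with 0.6 and 0.9 as a range.
- f, the share of trimester-1-exposed pregnancies surviving trimester 1 whose exposure reaches trimester 2: varied.
- True RR 1, and comparators on SOC for as long as they are pregnant.

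**Step 1: the plan's own figure.** The protocol gives no figure for this sensitivity analysis. Its sample size for pregnancy loss can be checked to confirm the 20% risk: n = (1/p + 1/(kp)) × (1.96 + 0.84)² / (ln 2.5)².
- 1:2 matching: (5 + 2.5) × 7.85 / 0.840 gives 71; stated 72.
- 1:3 matching: (5 + 1.667) × 7.85 / 0.840 gives 63; stated 61.

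Both agree closely. Simulating the protocol's own steps gives 82% power at 72 and 79% at 61.

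**Step 2: null RR for pregnancies exposed in trimester 1**, if comparators need SOC in at least the same trimesters.
- Exposed risk = L.
- A fraction (1 − Ls)f of exposed pregnancies reach trimester 2 still exposed. Their comparators survived trimester 1 and have risk q = L(1 − s)/(1 − Ls) = 0.04/0.84 = 0.048 at s = 0.8.
- The rest get comparators with risk L.
- Comparator risk = L[1 − (1 − Ls)f] + (1 − Ls)f·q = L[1 − (1 − L)fs].
- Null RR = 1/[1 − (1 − L)fs] = 1/(1 − 0.64f) at s = 0.8.

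**Step 3: add the late starters.** They are matched to survivors, as they should be, so both arms have risk q. Null RR = (0.8L + 0.2q)/(0.8 × comparator risk + 0.2q). The share of all comparators that must have survived trimester 1 is 0.8 × 0.84f + 0.2.

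| f (s = 0.8) | Comparator risk, trimester-1 group | Null RR, trimester-1 group | Null RR with late starters | Comparators that must have survived trimester 1 |
|---|---|---|---|---|
| 0.10 | 18.7% | 1.07 | 1.06 | 27% |
| 0.25 | 16.8% | 1.19 | 1.18 | 37% |
| 0.50 | 13.6% | 1.47 | 1.43 | 54% |
| 0.75 | 10.4% | 1.92 | 1.83 | 70% |
| 0.90 | 8.5% | 2.36 | 2.19 | 80% |

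For the trimester-1 group, s = 0.6 gives 1.05, 1.32 and 1.76 at f = 0.1, 0.5 and 0.9; s = 0.9 gives 1.08, 1.56 and 2.84. An individual-level simulation at s = 0.8 gave 1.19, 1.47 and 2.35 at f = 0.25, 0.5 and 0.9.

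**Step 4: how large could f be?** A dose x weeks after LMP2 (negative if before) gives exposure until x + 16. The protocol gives no trimester length. If trimester 1 ends 10 to 12 weeks after LMP2, exposure reaches trimester 2 whenever x is at least −6 to −4. With the monthly dosing described in section 7.2, that covers nearly every woman on treatment at conception whose pregnancy survives trimester 1. Women last dosed earlier within the 16-week look-back would not reach it.

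**Step 5: the other reading.** Suppose an identical trimester pattern is required, with SOC persisting into trimester 2 in a share g of comparators who survive trimester 1. If g = f, the null RR is 1.0. If f = 0.5 and g = 0.9 (s = 0.8), comparators with SOC in trimester 1 only are 0.16 early losses plus 0.84 × 0.1 = 0.084 survivors. Their loss risk is (0.16 + 0.084 × 0.048)/0.244 = 0.67. Comparator risk is 0.58 × 0.67 + 0.42 × 0.048 = 0.41, so the null RR is 0.20/0.41 = 0.49.

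**The case against.** Several objections stand.
- **Scope.** This is one sensitivity analysis among several. The main RR, the sample size and the power do not use this matching. For MCM, exposure is confined to trimester 1, so the condition adds little.
- **Late starters.** In the protocol's own example the exposed pregnancy must itself have survived trimester 1. Asking the same of comparators is sound and removes the immortal time conceded in section 9.9.
- **Wording.** The rule can also be read as requiring an identical trimester pattern, and then the bias may vanish or reverse (step 5).
- **Carry-over.** The rule that a trimester counts as exposed when the exposure period overlaps it is written for the exploratory by-trimester analysis. Section 9.7.5 does not say whether trimester exposure here includes the 16-week window, and a high f depends on that.
- **Purpose.** Matching only on SOC at LMP2 for everyone would largely drop what the analysis is meant to test.

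A reader might infer that most comparators are forced survivors, or that the analysis will produce a false signal near RR 2.5. The documents support neither as a general statement. The first needs f of roughly 0.5 or more, the second about 0.9, and the protocol gives neither f nor s. The 2.5 margin appears only in the study-size planning; no rule applies it to this result.

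None of this repairs the rule. On either reading, comparators are chosen on what happened after follow-up began.

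**Conclusion.** The point holds for Objectives 3-4 as a should-fix. If SOC is required in at least the same trimesters, the matching biases the pregnancy-loss RR upward under no effect. At L = 0.20 and s = 0.8 the null RR among trimester-1-exposed pregnancies runs from about 1.07 (f = 0.1) to 2.4 (f = 0.9), and slightly lower with late starters included. The size rests on f and s, both assumed. Higher f is plausible if the 16-week window defines trimester exposure here. If an identical pattern was meant, the direction is uncertain, but the match still conditions on the future. The main analysis is unaffected.

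**What to change.** Rewrite the matching rule in section 9.7.5:
- At the gestational day anifrolumab exposure starts (LMP2 if exposure is already present), match to unexposed pregnancies still ongoing and with recorded actual SOC use at that gestational age.
- Follow both from that day.
- Do not require SOC use in later trimesters for matching.
- Describe later actual SOC use, or enter it as a time-updated covariate in a time-aligned analysis.

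Under the assumptions above the null RR becomes 1.00: both arms have risk L when aligned at LMP2, and both have risk q when aligned after trimester 1. Alignment for late starters is kept.

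The cost is one paragraph and slightly more programming. The downside is that later SOC discontinuation is no longer matched on.
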